## 6.1.1. Tables and Listings

#### Tables

In general, data will be summarized by groups (i.e., by vaccine type [BNT162a1, BNT162b1, BNT162b2, BNT162c2 SD and BNT162c2 P/B] and cohort) and all cohorts combined for each type (cohort-total). Furthermore, selected cohorts may be combined. The cohorts and cohort-total will be presented in columns and the different vaccine types in different tables.

There may be additional total columns for younger (18 to 55 years) and older (56 to 85 years) subjects.

Descriptive summary tables as well as figures will be based on scheduled visits.

Continuous variables will be summarized by group using the following descriptive statistics: number of subjects with non-missing data (n), mean, standard deviation (SD), median, minimum (min) and maximum (max).

Descriptive statistics of titer and fold increase of titer will additionally include geometric mean and its two-sided 95% confidence interval (CI). The geometric mean titer (GMT) is calculated as the mean of the logarithm of the functional antibody titers, back-transformed into the original scale. Two-sided CIs will be obtained by calculating CIs using t-distribution for the mean of the logarithmically transformed assay results and transforming the limits back to the original scale.

Geometric mean fold rise (GMFR) is calculated as the mean of the difference of logarithmically transformed assay results (post vaccination time point – pre vaccination time point) and back-transformed into the original scale. Two-sided CIs will be obtained by calculating CIs using Student's t-distribution for the mean difference of the logarithmically transformed assay results and transforming the limits back to the original scale.

Categorical variables will be summarized by group presenting absolute and relative frequencies (n and %) of subjects in each category (including the category 'missing' if applicable).

Percentages will be calculated based on the number of subjects in the respective analysis set (N) as denominator if not stated differently. Percentages may be presented with exact 95% Clopper-Pearson CIs.

SDs as well as CIs will only be calculated if values of at least 3 subjects are available.

#### Listings

Important Case Report Form (CRF) data as well as all relevant generated and transformed variables together with the original data items will be listed. Separate listings will be provided for each vaccine type. Unless otherwise specified, cohort will always be included in listings, and listings will be sorted first by cohort, then by subject number and finally, if applicable, by visit number and/or a relevant date (e.g. date of onset of AE).

#### Programming

SAS® (version 9.4 or higher) programming will be performed according to Staburo GmbH standards as defined in the standards and related work instructions. Special attention will be paid to planning and performance of quality control measures as documented in the quality control plan for the analysis of this study (see also

#### **Analysis Sets**

The SCR will be used for disposition. The SAF will be used for analysis of safety and adverse events data. Some analyses of the adverse events will be repeated using the SAFB if the SAF and the SAFB sets differ. The IMM will be used for the analysis of immunogenicity data. The analyses of all vaccines may be repeated using the IMMPP if the two analysis sets differ significantly. This will be decided at the data review meeting.

If subjects by accident receive two different doses or vaccines, they will switch the group and will be displayed for each immunization with the corresponding group. For combined analyses, subjects who received two different doses will be assigned to the lower dose. Subjects who receive different doses as per protocol will be presented in their respective group.

Data of subjects who failed to complete all visits of the study (dropout or withdrawal) will be reported as far as their data is available.

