# 8.4 Treatment of overdose

Any dose of trial treatment above the planned dose specified in this protocol will be considered an overdose.

The sponsor does not recommend specific treatment for an overdose.

In the event of an overdose, the investigator should:

- Contact the sponsor's Medical Monitor immediately.
- Closely monitor the trial subject for any AE/SAE and laboratory abnormalities (at least for 7 d).
- Document the quantity of the excess dose as well as the duration of the overdose in the CRF.

Decisions regarding dose interruptions or modifications will be made by the investigator in consultation with the sponsor's Medical Monitor based on the clinical evaluation of the trial subject.

Clinical Trial Protocol including Amendments Nos. 01 to 09 BNT162-01 Page 77 of 113 Version: 13.0 Date: 12 JAN 2022

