#### Immunogenicity per-protocol set (IMMPP)

The immunogenicity per-protocol set is defined as all subjects included in the immunogenicity set that have no major protocol deviations as determined by the clinician.

Note: In all analysis sets, subjects will be assigned to the groups (i.e. vaccine type and cohort) according to the actual treatment they received ("as treated").

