#### 6.4.3. Adverse Events

#### Definition

For detailed information on adverse events see section 10.3 of the protocol.

Adverse events (AEs) will be coded using the Updated Version MedDRA® 23.0 including specific terms for COVID-19 to get a system organ class (SOC) and preferred term (PT) for each AE.

A treatment emergent adverse event (TEAE) is defined as any AE with an onset after the first immunization (if the AE was absent before the first immunization) or worsened after the first immunization (if the AE was present before the first immunization). AEs with an onset date more than 28 days after the last immunization will be considered as treatment emergent only if assessed as related to IMP by the investigator. AEs that cannot be determined to not be treatment emergent due to missing date or time will be defined as TEAE.

Clarification: To clarify the definition in the protocol, AEs with an onset date at the date of the first immunization will only be considered as treatment emergent if the AE occurred after the first immunization.

The TEAEs will be evaluated for the following time intervals, clarifying and harmonizing the intervals defined in the protocol:

- Prime immunization up to boost immunization or day 28 (inclusive) after initial immunization (whatever comes first)
- Boost immunization up to day 28 (inclusive) after boost immunization
- All TEAEs (regardless of relationship assessment) occurring from

- Prime immunization up to day 28 after boost immunization (inclusive).
- If no boost immunization, up to 28 days (inclusive) after prime immunization
- All TEAEs assessed as related through visit 10.

The intervals starting or ending with an immunization, will start or end with the date and time of the immunization. TEAEs are assigned to the time intervals according to their start date and time. AEs with missing date will be assigned to each of the respective intervals if it cannot be ruled out, that it belongs to the time interval.

Deviating from the protocol, the time intervals including 7 days after each immunization will not be analyzed.

AEs will be evaluated for the following time interval 'After Day 28 after boost or after prime (if no boost)':

All AEs (regardless of relationship assessment) occurring

- After day 28 after boost immunization
- o If no boost immunization, after 28 days after prime immunization

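### In tables that span both immunizations, a subject given two different doses by accident is counted at the lower dose, so an event after the higher dose appears in the wrong dose column

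*SAP*

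**What the plan says.** SAP section 6.1.1, under Analysis Sets, has three rules for subjects who receive more than one dose level.

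- Where the mixture is accidental, "they will switch the group and will be displayed for each immunization with the corresponding group".
- Then: "For combined analyses, subjects who received two different doses will be assigned to the lower dose".
- Planned mixtures are exempt: "Subjects who receive different doses as per protocol will be presented in their respective group". This covers Cohort 11 (3 µg prime, 30 µg boost).

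The note at the end of SAP section 5.1 sets the general principle for every analysis set: "subjects will be assigned to the groups (i.e. vaccine type and cohort) according to the actual treatment they received".

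The tables concerned are defined later. SAP sections 6.4.1 and 6.4.2 evaluate solicited reactions over the 7 days after prime, the 7 days after boost, and the two windows together. SAP section 6.4.3 evaluates TEAEs from prime to boost (or day 28), from boost to day 28 after it, and over the whole span from prime to day 28 after boost. The SAP does not say what it means by combined analyses and gives no reason for choosing the lower dose. SAP section 7.1, which lists changes to the protocol-planned analyses, does not mention the rule.

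**The concern.** The primary objective is to describe safety and tolerability, and SAP section 6.4 reports the primary endpoints by vaccine type and cohort. A rule that always sends a mixed-dose subject to the lower column misplaces events after the higher dose in one direction only. It does so whether the mistake was the higher dose or the lower one. An accidental dose above plan is a case the protocol itself marks out (section 8.4): "Any dose of trial treatment above the planned dose specified in this protocol will be considered an overdose". In a combined table, an event after such a dose would be charged to a dose that did not precede it. The same event would then sit under one dose in the boost table and under another in the combined table. With 12 subjects per cohort, a single subject is visible in the percentages.

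**Working it through.** **Inputs.** Cohort size is 12 (protocol Tables 1 and 2; section 9.2). Assumed for illustration: two cohorts of one vaccine at adjacent doses, one misdosed subject, one event after the higher dose, and no other events. The documents do not say how many subjects, if any, were misdosed.

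**The plan's own figure.** Protocol section 9.2 gives 85.8% as the chance of seeing a TEAE of 15% incidence at least once in 12 subjects. The formula is 1 − (1 − p)^n, and 1 − 0.85^12 = 0.8578, so the figure reproduces.

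**Case A: scheduled for the lower dose, boosted with the higher by mistake, event after the boost.** Intervals are exact (Clopper-Pearson) 95%.

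| Table | Lower dose | Higher dose |
|---|---|---|
| Boost only (SAP rule) | 0/11 = 0% (0 to 28.5) | 1/13 = 7.7% (0.2 to 36.0) |
| Both immunizations, SAP rule | 1/12 = 8.3% (0.2 to 38.5) | 0/12 = 0% (0 to 26.5) |
| Both immunizations, highest dose received | 0/11 = 0% (0 to 28.5) | 1/13 = 7.7% (0.2 to 36.0) |

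The lower-dose column changes by 8.3 − 0 = 8.3 points and the higher-dose column by 7.7 − 0 = 7.7 points. Rows 1 and 2, both produced under the SAP, place the same event at different doses.

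**Case B: scheduled for the higher dose, boosted with the lower by mistake, event after the higher prime.**

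| Table | Lower dose | Higher dose |
|---|---|---|
| Prime only (SAP rule) | 0/12 = 0% | 1/12 = 8.3% |
| Both immunizations, SAP rule | 1/13 = 7.7% | 0/11 = 0% |
| Both immunizations, highest dose received | 0/12 = 0% | 1/12 = 8.3% |

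The higher-dose column also falls from 12 to 11 subjects. The detection probability at 15% incidence becomes 1 − 0.85^11 = 0.8327, that is 83.3% instead of 85.8%.

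**Within-vaccine total.** In both cases the two cohorts together show 1 event in 24 subjects under either rule (12 + 12 = 11 + 13 = 24), so cohort-total columns do not change.

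**The case against.** Four points can be made for the plan.

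*The event is not lost.* A reader might infer that toxicity after a mistaken higher dose disappears from that dose's record. It does not. The rule just before the lower-dose rule keeps the subject under the dose given in prime-only and boost-only tables. All AEs and drug exposure are listed (SAP sections 6.4.3 and 6.7.1), and incorrect dosing is a candidate major deviation, which would be listed and summarized (section 5.2). This stands and limits the point to combined-interval tables. One gap remains: related TEAEs starting more than 28 days after the boost enter only the overall interval (SAP section 7.1), so they have no per-immunization table to set against it.

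*The term may mean something else.* SAP section 6.1.1 also speaks of combining cohorts, and in within-vaccine totals the assignment changes nothing. This is fair, since the term is undefined. But if it means pooled cohorts, the SAP has no rule for mixed-dose subjects in tables that span both immunizations, and one is needed.

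*Highest dose is also arbitrary.* A subject given two doses has no single treated dose, and highest-dose assignment would charge an event after the lower dose to the higher one. This is partly right. Reactogenicity is more plausibly due to the higher dose, and a separate line misattributes nothing.

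*Nothing is decided on these tables.* A reader might infer that the rule helps a higher dose to be selected. The documents do not support that: no hypothesis is tested, escalation rests on Safety Review Committee assessment of 48 h data (protocol sections 4.1 and 10.1.5), and protocol section 4.1 describes the BNT162b2 regimen as already determined. Misdosing should also be rare, because protocol section 6.4 has a second staff member confirm each dose.

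**Conclusion.** The point holds as a minor defect of attribution. Followed as written, and reading combined analyses as intervals that span both immunizations, the rule places an event after the higher dose in the lower-dose column. It departs from the as-treated note and contradicts the SAP's own per-immunization tables. One misdosed subject with one event changes a 12-subject column by about 8 percentage points; the exact intervals are wide and overlap, so this concerns accurate description and would not overturn a conclusion.

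The effect is confined to dose-level columns of combined-interval tables. Per-immunization tables, listings, within-vaccine totals and escalation decisions are unaffected, and Cohort 11 is exempt. If no subject was misdosed, the effect is zero. A separate gap is that the lower-dose rule gives no instruction for combined tables when a subject received two different vaccines.

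**What to change.** In SAP section 6.1.1, define combined analyses as those over intervals that span both immunizations, and replace the lower-dose sentence with rules to this effect:

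- *Safety:* subjects who by accident received two different doses of one vaccine are either assigned to the highest dose received, with a footnote, or shown on a separate footnoted line outside the dose columns.
- *Two different vaccines:* such subjects are shown per immunization only, and listed.
- *Immunogenicity:* in combined summaries, misdosed subjects are listed outside the dose-level columns.

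The cost is a few lines of SAP text and one derivation flag. Under highest-dose assignment, an event caused by the lower dose may be counted at the higher one. The separate line avoids this, at the price of one or two subjects standing outside the cohort columns.

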#### 6.1.2. Definitions and Derivations

#### **Unscheduled** visits

Unscheduled visits will not be included in the summary tables but will be included in the listings.

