### 8.2.4 Clinical laboratory tests

See Section 10.2 for the list of clinical laboratory tests to be performed at the times given in the SoA (Section 1.3).

The investigator must review the laboratory report, document this review with signature and date, and record any clinically relevant changes occurring during the trial in the AE section of the CRF.

All laboratory tests with values considered clinically significantly abnormal during participation in the trial should be repeated until the values return to normal or baseline or are no longer considered clinically significant by the investigator or the sponsor's Medical Monitor.

If such values do not return to normal/baseline within a period of time judged reasonable by the investigator, the etiology should be identified and the sponsor notified.

All protocol-required clinical laboratory tests (see Section 10.2) must be conducted in accordance with the trial site standard.

If laboratory values from non-protocol-specified laboratory assessments performed at the laboratory require a change in trial subject management or are considered clinically significant by the investigator (e.g., SAE, AE or dose modification), then the results must be recorded in the CRF.

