# 8.2.11 Subject hotline

Subjects will be provided with contact details for a Subject Hotline, which can be used to contact the trial site during their participation in the trial should they require guidance or should they experience any symptoms of illness. The reporting of any symptoms of illness, e.g., flu-like symptoms, may trigger diagnostic measures (including ad hoc site visits) at the discretion of the investigator. For guidance for specific AEs, see Section 6.6.3.

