#### Variables

Baseline is defined as last value prior to first dose of IMP, including unscheduled visits.

Change from baseline will be calculated as follows:

• Change from baseline = post-baseline assessment value – baseline assessment value.

Duration [days] will be calculated as follows:

• Duration [days] = last observation date – first observation date + 1

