#### Analysis

Clinical laboratory variables at each time-point and its change from baseline to each postbaseline time-point (for continuous variables) will be summarized using descriptive summary statistics for each parameter by group and cohort-total.

Number and percentage of subjects with low, normal and high clinical laboratory values at each time-point will be summarized for each parameter by group and cohort-total. The same table will be provided for the grading scheme (grades mild, moderate, severe and life threatening) for lymphocytes.

The number and percentage of subjects with CS abnormal, abnormal (not CS), normal and missing values will be summarized for each parameter by group and cohort-total.

Clinical laboratory values for each parameter will be summarized using shift tables from baseline to worst post-baseline value with respect to reference range values (low, normal, high) by group. Worst post-baseline might be in both directions. Each subject may be counted in the parameter high and in the parameter low category. A subject will only be counted in the normal category if

all post-baseline values are normal. If several post-baseline values are considered as worst post-baseline value, the first one is taken.

All clinical laboratory data will be presented in the data listings along with normal ranges Abnormal clinical laboratory values will be flagged in the listing.

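### The SAP's exclusion of unscheduled visits from summary tables conflicts with its worst-post-baseline laboratory shift table, and can tabulate a subject with an out-of-range value as normal

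*SAP*

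**What the plan says.** Three parts of the SAP bear on this.

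- **General rule.** SAP 6.1.2 (Unscheduled visits): "Unscheduled visits will not be included in the summary tables but will be included in the listings". SAP 6.1.1 (Tables) says the same from the other side: "Descriptive summary tables as well as figures will be based on scheduled visits".
- **Exception.** SAP 6.1.2 (Variables): "Baseline is defined as last value prior to first dose of IMP, including unscheduled visits". No matching exception is written for post-baseline values.
- **Laboratory analysis.** SAP 6.7.2: "Clinical laboratory values for each parameter will be summarized using shift tables from baseline to worst post-baseline value", using the categories low, normal and high. A subject may be counted as both low and high, and is counted as normal only if "all post-baseline values are normal". A separate count is described thus: "The number and percentage of subjects with CS abnormal, abnormal (not CS), normal and missing values will be summarized for each parameter". The SAP names no visit for that count.

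The protocol foresees laboratory samples outside the schedule. Section 8.2.4: "All laboratory tests with values considered clinically significantly abnormal during participation in the trial should be repeated". Section 8.2.11 says that symptoms reported to the hotline "may trigger diagnostic measures (including ad hoc site visits) at the discretion of the investigator". Section 8.11 allows extra blood for safety assessment after AEs or SAEs.

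**The concern.** A worst-value shift table is meant to show any excursion outside the reference range, whenever it occurred and whatever the investigator thought of it. If unscheduled samples are removed before the worst value is found, the table reports the worst *scheduled* value under a title that promises more. The error runs one way within a given direction: leaving values out can hide a low or a high result but cannot create one.

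The two sections also give a programmer contradictory instructions. SAP 6.7.2 read literally takes every post-baseline value; SAP 6.1.2 forbids some of them. Two competent programmers could produce different tables from the same data, and a reader of the report could not tell which rule had been used.

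The protocol's own plan for laboratory shift tables (section 9.4.5) contains no such exclusion, and SAP Appendix 1, which lists departures from the protocol, does not mention one.

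**Working it through.** The documents give no figure for this point, so the check is mainly a cross-reading, with arithmetic for scale.

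**1. When are safety bloods scheduled?** From the clinical laboratory rows of the protocol's schedules:

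| Schedule | Scheduled clinical laboratory blood |
|---|---|
| Table 6 (P/B, excluding Cohorts 11 to 14) | Visit 0, Days 1, 2, 8, 29, 50 |
| Table 8 (Cohorts 11 to 13) | Visit 0, Days 1, 2, 8, 29, 50 |
| Table 9 (Cohort 14) | Visit 0, Days 1, 8, 29, 50 |

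Nothing is scheduled between Day 8 and Day 29. The boost is on Day 22, so the first scheduled sample after it comes 29 − 22 = 7 days later, subject to the visit windows. Nothing is scheduled after Day 50. A transient excursion in these intervals can be seen only in an unscheduled sample, if one is taken.

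**2. What does each rule do with such a sample?** Take three hypothetical subjects, each with baseline in range.

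| Subject | Scheduled values | Unscheduled value | Under 6.1.2 | Under 6.7.2 read literally |
|---|---|---|---|---|
| A | all in range | low, between Day 22 and Day 29 | normal | low |
| B | low on Day 29 | repeat, lower still | low | low |
| C | high on Day 29 | low at an ad hoc visit | high | high and low |

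The rules disagree for A and C and agree for B. B is the typical repeat under protocol 8.2.4: the triggering value is already in the table, and a more extreme repeat in the same direction does not change a low/normal/high category.

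**3. Which tables are affected?**

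- *Laboratory shift table*: yes, because it is defined across visits.
- *Clinically significant / not clinically significant count*: only if it is produced across visits. The SAP does not say; protocol 9.4.5 describes its version per parameter and visit.
- *Low/normal/high table and lymphocyte grades*: no. Both are by time-point, where restricting to scheduled visits is ordinary practice.

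**4. Weight of one subject.** 1/12 = 8.3 percentage points in a dose-ranging cohort; 1/20 = 5.0 in Cohort 14; 1/30 = 3.3 in Cohorts 11 and 13; 1/90 = 1.1 in Cohort 12.

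**5. Illustration under an assumption.** Protocol Table 10 uses 1 − (1 − p)^n for the chance of seeing an event at least once. With n = 12 and p = 15% this is 1 − 0.85^12 = 85.8%, which reproduces the protocol's figure. That table concerns TEAEs; the formula is borrowed here only for scale. Let q be the share of subjects with an excursion whose only out-of-range value is unscheduled. The chance that the shift table shows at least one case becomes 1 − (1 − p(1 − q))^n. The documents give no q, so a range is shown:

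| n, p | q = 0 | q = 10% | q = 25% | q = 50% |
|---|---|---|---|---|
| 12, 15% | 85.8% | 82.5% | 76.1% | 60.8% |
| 30, 5% | 78.5% | 74.9% | 68.2% | 53.2% |
| 90, 5% | 99.0% | 98.4% | 96.8% | 89.8% |

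For example, n = 12 and q = 25% gives 1 − (1 − 0.15 × 0.75)^12 = 76.1%.

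**The case against.** The strongest reply is that the values that matter clinically are not lost. Protocol 8.2.4 requires clinically relevant laboratory changes to be recorded as AEs, and 10.3.1.7 says the same of clinically significant findings. SAP 6.4.3 assigns AEs to intervals by onset date and time, not by visit, and tabulates treatment-emergent AEs by preferred term, grade and relationship, with a separate summary for AEs after Day 28. A clinically significant result from an ad hoc visit therefore has a route into summary tables, as a laboratory term or as the diagnosis or symptom behind it. This stands, and it limits the consequence. It does not repair the shift table: under protocol 10.3.1.9 an abnormality not considered clinically significant need not be an AE, and that result would then appear only in the listings, where abnormal values are flagged.

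It can also be said that the specific wording of 6.7.2 should override the general rule, so that nothing is omitted. That reading is possible, but the SAP does not state it, and where its authors wanted unscheduled values (baseline) they said so. The baseline rule itself is unobjectionable; it follows protocol 9.4.1.

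Several stronger readings are tempting and are not supported:

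- *Unscheduled samples are the ones most likely to hold the worst value.* The documents do not say so. It is plausible for samples taken after an AE and weak for repeats, as subject B shows.
- *All safety summaries are biased.* Vital signs have no worst-value or shift table (SAP 6.7.3), lymphocyte grades are by time-point, and local and systemic reactions are analysed by date and time interval (SAP 6.4.1 and 6.4.2).
- *The loss is 8.3 percentage points.* That is the weight of one subject in 12, not an estimate of how many are affected.

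**Conclusion.** The conflict between SAP 6.1.2 and 6.7.2 is real and should be resolved in the text. Its firm core is the laboratory shift table; it extends to the clinically significant / not clinically significant count only if that count is not by visit. If 6.1.2 governs, a subject whose only out-of-range value is unscheduled is tabulated as normal.

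The number of such subjects cannot be known from the documents, and it may be zero in many cohorts. The conclusion assumes only that some unscheduled safety samples are taken and recorded, which the protocol foresees, and that SAP 6.1.2 is applied as written.

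Severity is minor to moderate. A reader might infer that the safety conclusions cannot stand until this is changed. The documents do not support that: the trial tests no hypothesis, the laboratory tables are further safety analyses rather than primary endpoints, and dose progression rests on the Safety Review Committee's direct review of 48 h data. The point is still more than a missing detail, because the present rule can only move subjects out of the low or high category and is easily corrected.

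**What to change.** Add to SAP 6.1.2, with a cross-reference in 6.7.2, a sentence such as: *Unscheduled post-baseline laboratory values are excluded from by-visit summaries, but are included when deriving the worst post-baseline value for the shift table and in any count of clinically significant and not clinically significant abnormalities that is not presented by visit.* State in 6.7.2 whether that count is by visit or over the whole post-baseline period, and qualify the matching sentence in 6.1.1 so that it does not reintroduce the conflict.

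The cost is one sentence and a small programming change. No new data are needed: the SAP already plans to list unscheduled visits, so recorded values are available. Results of non-protocol laboratory assessments that never reached the CRF (protocol 8.2.4 requires entry only if they change subject management or are clinically significant) would remain outside the table.
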